12.1 Visit 1 Baseline visit

Patients presenting with symptoms suggestive of pulmonary TB to one of the study clinics will be invited to be screened for inclusion in the study. Before any study-specific screening procedures will be performed, all patients will sign and date (or thumbprint) the latest version of the ICF. Illiterate participants will be encouraged to have a witness present.

After informed consent has been obtained, the patient will receive a study number. The ICF will be labelled with the study number. A primary health care nurse or dedicated researcher staff will administer a questionnaire (V1-D1) and ask the patient about their contact details and the contact details of a trusted proxy (locator form). In addition, 5 to 10% participants per site will be invited to answer a socio-economic questionnaire about income, cost of care seeking, productivity losses, diagnostics and treatment (V1-D1-SE). For these participants a face-to-face interview may be conducted.

Depending on the clinic, the patient will receive a diagnostic work-up according to the national algorithm (smear microscopy and/or off-site Xpert testing) or the study intervention (Truenat

Protocol short title: TB-CAPT CORE Truenat trial

Protocol Number: TB041-3/1 -MZ

Protocol Version: 4.0 - CONFIDENTIAL - Page 40 of 57

platform/TB assays on site). Further diagnostic investigations and TB treatment initiation will be as clinically indicated. All clinical care and further investigations will be provided within the governmental health care service. Patient details (including name, sex, age, and study-ID) will be documented in a study register, which will remain at the clinic. All patients will receive a study card with their details (including name, sex, age and study number and enrolment date) to take home with them. They will be asked to show the card if they present to the clinic again.

12.2 Visit 2: Day 7

All participants will be called by telephone 7 days after enrolment (between day 8 and day 21 after enrolment). Three attempts will be made to contact a participant by phone. If these attempts are unsuccessful the trusted proxy will be contacted to find out about the participant's whereabouts and arrange for a return call by the participants or a home visit. A home visit will be conducted for those participants who cannot be reached by phone.

The questionnaire administered by phone or face-face (V2-D7 CRF) will include questions about symptoms, whether TB was diagnosed (and by what means) and treatment started and if the participant had accessed another health care provider.

12.3 Visit 3: Day 60

All participants will be called by telephone 60 days after enrolment (between day 61 and day 90 after enrolment). Three attempts will be made to contact a participant by phone. If these attempts are unsuccessful the trusted proxy will be contacted to find out about the participant's whereabouts and arrange for a return call or a home visit. A home visit will be conducted for those participants who cannot be reached by phone.

The questionnaire administered by phone or face-face (V3-D60) will include questions about symptoms, whether TB was diagnosed (and by what means) and treatment started and if the participant had accessed another health care provider and how often.

- CONFIDENTIAL - Page 41 of 57

13. STATISTICAL CONSIDERATIONS

13.1 Populations to be analyzed

Intent-to treat (ITT) population: The ITT population will consist of all enrolled patients in the groups to which randomly assigned to intervention and controls. Patients with missing outcome data at days 7 and 60 will be assumed to not have started treatment.

Per-Protocol (PP) population: The PP population will consist of all patients who fulfil the protocol in the terms of eligibility, interventions, and outcome assessment without any major protocol deviation.

The Statistical Analysis Plan (SAP) will define the criteria for the exclusion of patients from any of the above-mentioned analysis populations and will be finalized prior to database lock. The SAP will also provide a detailed summary of the analysis methodology for each of the outcomes of the trial.

13.2 Design considerations

Matched paired design and stratification have been considered as a study design. In fact, matched paired design can be regarded as an extreme form of stratification. Stratification involves the grouping of available clusters into strata that are expected to be similar in outcome. We have decided for stratification for the following reasons³³:

- Fewer degrees in freedom are lost which is effective considering the relative low number of clusters per arm (10 .. 15).
- Adjustment for covariates via (generalized) linear models is possible
- Single missing clusters can be handled without losing a pair.

13.3 Randomization

See section 9.5.2

13.4 Descriptive statistics

Baseline characteristics, such as demographic and analytical data will be summarized using descriptive statistical methods. Continuous data will be summarized using the mean, the median, standard deviation, the range (minimum and maximum value). Categorical values will be summarized using frequency counts and percentages.

Time to TB treatment initiation for those with microbiological confirmation	Participants with microbiological confirmed TB starting treatment	Person Time at risk	Visit 2 telephone call (V2-D7) Visit 3 telephone call (V3-D60) Study TB outcome worksheet		
Time to TB treatment initiation and for all participants	tiation and for all treatment		Visit 2 telephone call (V2-D7) Visit 3 telephone call (V3-D60) Study TB outcome worksheet		
Number and proportion of participants with ongoing TB treatment outcome	Ongoing TB treatment outcomes (on TB treatment at 60 days)	Participants diagnosed with TB Participants diagnosed with TB clinically Participants diagnosed with TB microbiologically	Visit 2 telephone call (V2-D7) Visit 3 telephone call (V3-D60) Study TB outcome worksheet TB treatment register		
Cost of diagnosis and treatment	Total cost to participants (among participants who respond to the costing survey)	Not applicable	Visit 1 extended questionnaire (V1-D1-SE)		

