will allow creating lists of study-IDs for locator forms to be retrieved and follow-up to be coordinated. A proportion of participants (5-10%) will be sampled, by selecting every tenth participant, across intervention and control clinics and across both countries to administered all of the questions of the baseline questionnaire plus some additional questions about costs of care-seeking. The data will be documented on the V1-D1-SE CRF. All clinics will be given a list of study-ID numbers identifying those participants who will be asked to answer the V1-D1-SE CRF before the start of enrolment.

Sites, which have the capacity to perform real-time data entry into electronic tablets, will be able to do so (as an alternative to paper-based CRFs).

Visit 2 (Day 7) and Visit 3 (Day 60) interviews will be conducted between days 8-21 and 61-90 post enrolment, respectively. Three attempts will be made to contact the participant. If the participant cannot be reached, the trusted proxy (documented on the locator form) will be contacted and asked about the participant's whereabouts. The trusted proxy will be asked on how best to contact the participant (i.e., other phone number or home visit). A home visit will be conducted for participants that cannot be reached by phone. A maximum of three home visit attempts will be made. Visit 2 and Visit 3 interviews will be recorded on paper-based CRFs (V2-D7, V3-D60) and entered electronically. Face-to-face visits may be considered for the Visit 3 interviews if a participant was sampled for a more extended socio-economic questionnaire (see above and below).

Only the study-ID and not the participant's name will be entered on the Truenat platform when a sample is tested. Pseudonymised Truenat TB assays results will be automatically uploaded to a secure, encrypted server at FIND using a Global SIM card on each Truelab micro PCR device in the intervention clinic on a regular basis using a File Transfer Protocol (FTP) or a similar system. This data maintains participant's confidentiality thereby ensuring subject's anonymity. Laboratory results such as smear microscopy or off-site Xpert MTB/RIF results will be captured by the research team supervisor and recorded in the study TB outcome worksheet.

Assay data (rates of non-determined results) and device data (instrument failures) will be securely uploaded to the FIND server and access by the trial data manager. Maintenance logs will be reviewed at the end of the study.

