9.11 Data collection and handling

There will be a maximum of three questionnaires administered per participant: at Visit 1 (baseline; V1-D1 or V1-D1-SE), Visit 2 (Day 7; V2-D7) and Visit 3 (Day 60; V3-D60 or V3-D60-SE). All interviews will be documented on paper CRFs entered electronically, either centrally at the four sites, or at the clinics, into the OpenClinica eCRF/data base located at the LMU. Direct electronic data entry will be supported if a research site has the capacity to do that. The paper CRFs (V1-D1) will be retrieved from clinics on a weekly basis and stored at the central site or entered at the clinic. Data entry of V1-D1 will need to be entered within 6 days of enrolment as it is particularly critical to support the conduct of the V2-D7 phone calls.

V2-D7 and V3-D60 questionnaires will be administered mainly by phone by the research team, entered into the database and filed and stored centrally at the sites. For a subset of participants (approximately 50 per site) a more detailed socio-economic questionnaire (V1-D1-SE) will be conducted at baseline and at the last visit (V3-D60-SE). For those participants the Visit 3 questionnaire may be administered face-to-face.

In addition, details (study-ID, name, sex, age, date of enrolment) of each participant will be documented in a study register, which will stored in a secure location by the site until 10 years after the end of the study unless local regulations or institutional policies require a longer retention period. The study register will be compared with the TB registers and clinic records to ascertain diagnostic results (such as smear results in the standard of care clinics), TB registration number and TB initiation dates. This will be documented on the study TB outcome worksheet. The completed worksheet will be retrieved at the end of the study, entered electronically and stored centrally.

Data on number of contact attempts, contact information provided by trusted proxy, date and location of home visits will be documented on paper in free text. This information will not be entered and stored centrally.

All paper forms (including consent form) will be stored in secure and locked cupboards with only authorised person having access to the forms. The electronic database will not include any names, but only study numbers. The OpenClinica Enterprise version 4.0 database will be secure, password protected and regularly backed-up. Only authorised people will have access to the database.

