The investigator will also withdraw a patient upon request of the sponsor or if the study is terminated as a whole. Participants who decide to withdraw or who have been withdrawn from the study will not be replaced. No further follow-up will be conducted after the withdrawal.

Visit 1 Baseline visit

Patients presenting with symptoms suggestive of pulmonary TB to one of the study clinics will be invited to be screened for inclusion in the study. Before any study-specific screening procedures will be performed, all patients will sign and date (or thumbprint) the latest version of the ICF. Illiterate participants will be encouraged to have a witness present.

After informed consent has been obtained, the patient will receive a study number. The ICF will be labelled with the study number. A primary health care nurse or dedicated researcher staff will administer a questionnaire (V1-D1 CRF) and ask the patient about their contact details and the contact details of a trusted proxy (locator form). In addition, a random sample of 5-10% of participants per site will be invited to answer a socio-economic questionnaire about income, cost of care seeking, productivity losses, diagnostics and treatment (V1-D1-SE CRF).

Depending on the clinic, the patient will receive a diagnostic work-up according to the national algorithm (smear microscopy and/or off-site Xpert testing) or the study intervention (Truenat platform/TB assays on site). Further diagnostic investigations and TB treatment initiation will be as clinically indicated. All clinical care and further investigations will be provided within the governmental health care service. Patient details (including name, sex, age and study-ID) will be documented in a study register, which will remain at the clinic. All patients will receive a study card with their details (including name, sex, age and study number and enrolment date) to take home with them. They will be asked to show the card if they present to the clinic again.

Visit 2: Day 7

All participants will be called by telephone 7 days after enrolment (between day 8 and day 21 after enrolment). Three attempts will be made to contact a participant by phone. If these attempts are unsuccessful the trusted proxy will be contacted to find out about the participant's whereabouts and arrange for a return call by the participants or a home visit. A home visit will be conducted for those participants who cannot be reached by phone.

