food costs incurred while in hospital, money spent buying any special foods). Indirect costs will be estimated as the opportunity cost of time spent seeking care (from the time of symptom onset to the time of treatment initiation), plus any lost productivity due to illness. Additional information from the scientific literature will be used to estimate costs that are not directly estimated (e.g., hospitalization costs, costs of TB treatment).

The total cost for each patient will be estimated as the sum of direct and indirect costs, and the mean cost will be taken as the sum of these total costs, divided by the number of patients.

Number of lost working days

We will use patient interviews to record the self-reported number of working days lost due to TB illness in both arms. This will be directly estimated; no additional statistical methods will be used. 95% confidence intervals will be calculated assuming a Poisson distribution.

Monthly earnings

To estimate loss in income, we will record the number of missed working days or missed working hours owing to TB illness, from the time of symptom onset to the time of treatment initiation. This number of days/hours will be multiplied by the average daily/hourly wage of employed laborers in each country to estimate the monthly earnings lost as a result of seeking care. If the patient does not have formal employment but works informally, e.g., as an agricultural worker, we will use their self-reported reduction in productivity (as a percentage of total productivity) over the course of the past year. This number will be multiplied by the average agricultural wage/earnings in each country and reported on a monthly basis. We will then calculate the mean monthly earnings lost as the sum of lost income (as described above), divided by the number of participants from which those data are obtained.

• Unit costs of diagnosis and treatment, modified societal perspective

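### Protocol Table 1 derives the patient-cost endpoint from the enrolment-day form alone, although Protocol 9.11 plans a day-60 form that Table 1, the schedule of events and the SAP all leave out

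*Protocol*

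**What the plan says.** Table 1 in Protocol 13.5 sets out how each endpoint is derived. Its last row, on the cost of diagnosis and treatment, has the numerator "Total cost to participants (among participants who respond to the costing survey" and one source: "Visit 1 extended questionnaire (V1-D1-SE".

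Several other places agree with that row:
- The schedule of events lists the socio-economic form at Day 1 only. Its Day 60 row names the plain V3-D60 form.
- Protocol 10.1 puts costs of care and loss of income under Visit 1. Protocol 10.2 and 12.3 list no cost items for Visit 3.
- SAP 3.1 says, under Visit 1, that "a random sample of 5-10% of participants per site will be invited to answer a socio-economic questionnaire". Its Visit 3 text mentions no costs, and V3-D60-SE is named nowhere in the SAP.

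Two places in the Protocol say something different. Section 9.11 states that for a subset "a more detailed socio-economic questionnaire (V1-D1-SE) will be conducted at baseline and at the last visit (V3-D60-SE", and it lists the last questionnaire as "Visit 3 (Day 60; V3-D60 or V3-D60-SE". Section 9.8 adds: "Face-to-face visits may be considered for the Visit 3 interviews if a participant was sampled for a more extended socio-economic questionnaire".

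On the analysis, Protocol 13.6 plans stratum-adjusted comparisons of cost. SAP 2.2 states two-sided hypotheses on the mean difference, intervention minus standard of care, for patient costs, lost working days and monthly earnings. SAP 4.3 includes in indirect cost "the opportunity cost of time spent seeking care (from the time of symptom onset to the time of treatment initiation", plus productivity lost through illness.

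**The concern.** The intervention is on-site testing with rapid results and same-day treatment (Protocol 9.2). Any saving it brings to patients, such as fewer return trips or fewer lost working days, falls after the enrolment visit. A form completed at that visit mostly records what the patient spent before reaching it. People already diagnosed with TB or already on TB treatment are excluded (Protocol 9.7.2), so the costs of diagnosis and treatment within the trial have largely not yet arisen.

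An analyst who follows Table 1 would therefore test for an arm difference mainly in costs that the intervention could not have changed. Differences in those costs reflect chance or clinic mix. A null result could be reported as no cost saving for patients when the saving had not been measured. The same patient costs feed the unit costs and the incremental cost-effectiveness ratio under the SAP's modified societal perspective.

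**Working it through.** The plan states no cost figure, so there is nothing to reproduce. The check sets the passages side by side and follows the expected mean difference.

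**Step 1. Which costs can each form see?**

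| Cost component | V1-D1-SE (enrolment, window under 48 hours) | V3-D60-SE (days 61 to 90) |
|---|---|---|
| Care-seeking before enrolment | yes | not needed |
| Costs on or next to the enrolment day | possibly some | yes, if the form asks |
| Return visits, later tests, time to treatment start | no | yes, if the form asks |
| Working days lost after enrolment | no | yes, if the form asks |

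The condition in the last column matters, because the documents do not describe the content of V3-D60-SE. That it repeats the cost questions of V1-D1-SE is an assumption.

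**Step 2. What does the mean difference estimate?** Write a participant's total cost as B + P, where B is cost before enrolment and P is cost after it. Then

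E[B + P | intervention] − E[B + P | SOC] = (difference in B) + (difference in P).

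If the arms enrol comparable patients, the first term has expectation zero and the second carries the effect.

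- With V1-D1-SE as the only source, the data contain B and at most the small part of P that falls in the Visit 1 window. Most of the second term is lost.
- With both forms, the data contain B + P. The expected mean difference is then the full difference in P. Including B leaves that expectation unchanged. It affects only the variance, Var(B) + Var(P) + 2Cov(B, P), and adjusting for B can recover precision.

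**Step 3. Does the enrolment-day form match the SAP's own window?** The window in SAP 4.3 closes at treatment initiation, and the endpoint in Protocol 9.6.2 covers diagnosis and treatment. An enrolment-day form can reach that closing point only for a participant who starts treatment within the Visit 1 window. The stated source and the stated window do not fit each other.

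**Step 4. How many participants are involved?**
- Protocol 9.11: about 50 per site × 4 sites = 200.
- Protocol 9.8 and SAP 3.1: 5% of 4200 = 210; 10% of 4200 = 420.
- Per clinic, with 28 clinics: 200/28 = 7.1; 420/28 = 15.

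This is a head count only. Without cost means and standard deviations it says nothing about power.

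**The case against.** The strongest reply is that post-intervention costs are planned for. Protocol 9.11 provides a day-60 socio-economic form for the same subset, and 9.8 foresees an extended Visit 3 interview. On that view Table 1 merely omits a source. This stands, and it rules out a stronger reading that a reader might draw from Table 1 taken alone: that the comparison cannot show an effect, or that its expected difference is exactly zero. Neither follows, for three reasons:

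- The day-60 form is planned, so the omission can be corrected.
- The Visit 1 window is under 48 hours, the intervention aims at same-day results and treatment, and Protocol 12.1 says that the questionnaire also covers diagnostics and treatment. Some early costs may be caught.
- SAP 4.3 fills in costs that are not measured directly, such as hospitalisation and TB treatment, from the literature. How these are assigned to each arm is not stated, so a difference of zero is not established.

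A reader might also infer that counting from symptom onset dilutes the effect. For an absolute mean difference it does not (Step 2); it adds noise. Nor do the documents support saying that most costs precede enrolment, or that their variance is large relative to the effect, since they give no cost figures.

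Table 1 has also suffered in text extraction. The cost row reads cleanly, however, and the schedule of events and SAP 3.1 make the same omission independently.

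The reply does not remove the contradiction. The table that governs derivation, and the SAP that governs analysis, both leave out the only instrument able to measure most of the effect.

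**Conclusion.** The plan is wrong as written on a secondary endpoint and should be corrected. Followed literally, Table 1 would have the arm comparison rest largely on pre-intervention costs and miss most post-enrolment costs of diagnosis and treatment. The error is conditional: it disappears if the analyst uses the form planned in Protocol 9.11, but neither Table 1 nor the SAP tells the analyst to do so.

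The size cannot be given in money or power. The scope is the patient-cost comparison, the lost-working-days and earnings comparisons that rely on the same questionnaire, and the patient-cost part of the cost-effectiveness ratio. The health-system costs, the effectiveness component and the primary analysis are unaffected.

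The conclusion rests on two assumptions: that V1-D1-SE is completed at or close to enrolment, as the schedule of events indicates, and that V3-D60-SE records costs and lost days, which the documents do not confirm.

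**What to change.** Reconcile the passages as follows:

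1. Add V3-D60-SE to the Table 1 cost row, to the schedule of events, and to SAP 3.1 and 4.3, as the source for between-arm patient costs and lost working days. State which costs come from which visit.
2. Confirm that V3-D60-SE records these items, and describe its content in the SAP.
3. Base the arm comparison on costs accrued after enrolment, up to the day-60 interview, and use the pre-enrolment costs from V1-D1-SE as a baseline covariate to gain precision.
4. Keep total costs from symptom onset for descriptive reporting and for the unit-cost work.
5. State how literature-based costs are assigned in each arm.

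Items 1, 2, 4 and 5 are wording if the form exists with the needed content. Item 3 also redefines the compared quantity, so it should be settled before any comparison of costs by arm; SAP 1.2 allows the cost endpoints to be analysed while the study is running. If the day-60 form turns out not to record costs, the report should say that patient costs after enrolment were not measured, and should not present the enrolment-day comparison as an effect of the intervention.
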